6.1 Risks

Potential risks are as follows:

- Because the research covers the subject of depression, emotionally sensitive subject matter may be discussed. This may be emotionally distressing to individuals in the study.
- Although we will strive to maximize the cultural sensitivity in delivering the proposed interventions, it is possible that certain individuals' explanatory models of their conditions will be incompatible with our proposed interventions. This has the potential to upset study subjects.
- Although we will make every effort to store data in a secure and confidential manner, in concordance with IRB approval, breeches of confidentiality may occur accidentally.
- On rare occasion, information may be obtained that may require mandatory reporting (for example, if a mother divulges that her boyfriend abuses her children). Although we have developed protocols to address such scenarios, they will invariably be upsetting.

6.2 Potential Benefits

The subjects involved in the study stand a reasonable chance of benefiting from both interventions, as both have RCT-level evidence of effectiveness. This study follows from greater than 10 years of prior work documenting its safety when conducted by the current group of investigators. Individuals not directly involved in this work stand the opportunity to benefit from the knowledge we gain from the study.

6.3 Analysis of Risks in Relation to Benefits

The potential long-term benefits of this study plan outweigh its risks. Determining effective therapies and prevention strategies for maternal depression—particularly strategies accessible to low-income populations—represents an opportunity not only to help depressed women, but also to enhance developmental outcomes for their children.

7 Study Subject Selection

7.1 Subject Inclusion and Exclusion Criteria

Inclusion Criteria	Exclusion Criteria

• Woman is pregnant and receives prenatal care at BMC; or is biological mother of 0 to 18-month-old child receiving care at BMC pediatric primary care clinic• Woman has EPDS score ≥ 10 (the most common cutoff used in studies included in the USPSTF report [2])• Woman comfortable speaking and receiving information in English or Spanish	
• Woman under 18 years of age• Woman endorses suicidality• Woman exhibits signs of psychosis or is cognitively limited ^a

• Woman had only one mental health care appointment in the last 3 months OR, if more than one appointment, woman has no upcoming appointments.	
--	--

8 Study Intervention

We are comparing 2 interventions in this trial: Engagement-Focused Care Coordination and PSE.

In Engagement-Focused Care Coordination, the brief intervention is the Engagement Interview, which is designed to help engage participants in mental health care. The Engagement Interview is NOT a therapeutic or preventive intervention in and of itself. In delivering the Engagement Interview, Bachelor-level providers meet one to two times for 45-60 minutes with women who screen positive for depression, and use techniques of shared decision-making to help mothers process the results of the screen; explore treatment options; and connect with formal mental health services. Engagement Interview training will be based on existing manualized protocols.

In PSE, problem solving sessions are one-on-one, workbook-based interactions that typically last 30 to 45 minutes. Sessions are delivered in the home, during lunch breaks from work, or in the clinic. A full course involves 6 sessions, delivered weekly or biweekly. The PSE training curriculum takes place over the course of a few weeks. After a two-day workshop, in which trainees will receive didactic instruction, they will complete five learning cases that will be audiotaped and reviewed.

9 Study Procedures

Please see the Appendix for the Schedule of Events.

The entire study duration will last from 5/1/2017 to 4/30/2020. However, the duration of subject participation will be 12 months for each subject. Here, we will describe all study procedures, including recruitment, screening, interventions, and follow-up.

Recruitment Procedures

In the outpatient setting, recruitment and enrollment into this trial will be linked to existing clinical systems in BMC's Pediatric Primary Care Clinic (Department of Pediatrics) and BMC's Prenatal Clinic and Postpartum Unit (Department of Obstetrics/Gynecology). Specifically, recruitment procedures will center around existing depression screening activities, common to both clinic sites; and embedded behavioral health services, which are a part of the current standard of care within Prenatal Clinic. Most importantly, all pregnant women seeking care in BMC's prenatal clinic and all mothers of young children seeking care in BMC's primary care pediatric clinic are screened with the EPDS - which is the primary instrument that determines eligibility into the PCORI study.

After a woman checks in for a prenatal appointment with Ob/Gyn or for a Pediatric appointment for her child, while waiting to be called into an exam room, she is screened for depression with the EPDS (attached). Upon completing the screen, the mother is informed of her score, its clinical significance, and treatment options (i.e. treatment options that are unrelated to the study). As the principal recruitment mechanism into the study, we will embed a "study option" into this clinical algorithm for all

those with EPDS scores ≥ 10 . Specifically, the possibility of learning more about the study will be presented as part of a menu of options to receive behavioral health services. If the mother expresses interest in being contacted for follow-up, she will provide contact information to the clinic staff member to be shared with the study team.

Once alerted that there is a new, EPDS-positive woman who is interested in follow-up, the study team member of the study team will review the mother's medical record for study eligibility, and will contact the mother soon thereafter to explain the study in detail and do further screening. We feel that is it appropriate for the staff member to review limited fields in the EHR (participant's age, child's age, participant's insurance status, address, past and upcoming behavioral health appointments, language, and visit type on the date of the EPDS screen) because this will allow for the determination of appropriate exclusion criteria with the least burden to the potential participant.

Further, if the mother is ineligible for the study after this further screening, the study team member will offer to connect the mother to existing clinic services. If she is eligible for the study, the team member will arrange with the mother a meeting in which consent, final eligibility determination, baseline, and randomization will take place.

In the inpatient setting, recruitment and enrollment will occur on BMC's post-partum floor. The eligibility criteria for this new postpartum population will be the same as our existing participants. The details of our approach are as follows:

1. Low literacy, language-appropriate, written information about the study (provided as an attachment in the application) will be provided to all families in their welcome packet to BMC's labor and delivery services.
2. Study RAs will confirm with hospital staff that the families have received the packet; once that has been confirmed, RAs will approach families according to the recruitment script attached to the application and entitled "Recruitment Script – Postpartum Packet".
3. Study staff will confirm both the mother's and baby's health status with hospital staff prior to introducing themselves to the mother for potential participation in the study.
4. Approaching mothers will occur in the postpartum unit, in concordance with guidelines from hospital staff. If the infant is hospitalized in the NICU or the inpatient ward, it is possible that will be approaching the mothers in these areas.
5. Consistent with other BMC studies, we will give potential subjects 24 hours after a vaginal delivery as a recruitment time frame and 48 hours after a c-section.
6. In the event of an early discharge, RAs will get permission from hospital staff to call the mother directly by phone. RAs will only call the mother if either the RA had made contact with the mother and explained the study, if the hospital staff member talked to the mother about the study, or if the staff member can confirm that the mother received her welcome packet.
7. Once the RA has made contact with the potential participant, all procedures will mirror what is already written in the study protocol.

Screening Procedures

In the outpatient setting, the first stage of screening will occur as part of existing clinic practice. After a woman checks in with Ob/Gyn or for a Pediatric appointment for her child, she will be screened for depression with the EPDS. If she scores a 10 or above, she will be presented with a menu of treatment options (according to clinic protocols), among which learning more about the study will also be offered as an option. If the woman expresses interest in being contacted for follow-up, clinic staff will ask her to provide contact information to pass along to the study team.

Once her contact information has been shared with the study team, a study team member will perform eligibility screening via the mother's medical record. We will do so in order to minimize unnecessary contact with subjects who are ultimately not eligible, and to minimize the time burden experienced by potential subjects on the phone with the study team. From the mother's medical record, the study team will gather the following: maternal age, child's age (if mother was recruited from the pediatric clinic), maternal health insurance type, maternal address, mother's past and upcoming behavioral health appointments, and the visit type on the date of the EPDS screen. If the mother is ineligible based on the medical record review, the team will connect her to existing clinic services. If the mother is eligible after the record review, the team will explain the study in more detail and ask for verbal consent to administer a few additional screening questions. These screening questions will ask about fluency in English or Spanish, whether the mother is currently receiving behavioral health services, and her pregnancy status. If the mother is ineligible based on any of her responses, the study team will explain that she is not eligible for the study at this time and offer to connect her to existing clinic resources. If the mother is eligible based on her responses, the study team will arrange a meeting in which written informed consent, final eligibility determination, baseline, and randomization will take place.

In the inpatient setting, the first stage of screening will occur when the research staff member reviews the daily census of the postpartum unit. The research staff will review: the mother's age, maternal health insurance, maternal address, mother's phone number, and mother's past and upcoming behavioral health appointments (if available). The second stage of screening will occur when the research staff member approaches the mother per the recruitment protocol. If the mother agrees to be screened (verbal consent), the staff member will administer the EPDS in-person, as well as the verbal eligibility screen. If she scores less than a 10 or scores a 10 or greater but fails the verbal screen, she will be informed that she is not eligible for the study. If she scores a 10 or above and passes the verbal screen, she will be informed that she is eligible for the study and the study team will arrange a meeting in which written informed consent, final eligibility determination, baseline, and randomization will take place.

At the meeting for informed consent, the final stage of screening will take place. After written informed consent, study staff will administer the MacArthur Competence Assessment Tool for Clinical Research (MacCAT-CR) and a suicide screen. For safety reasons, mothers who endorse suicidality at baseline or have disordered thinking will be excluded from the study at this point. Subjects who are eligible after consent will go on to complete the baseline interview and randomization. A safety protocol for managing suicidal ideation is attached to the application.

Intervention Procedures

Following randomization, assigned providers from either intervention arm will reach out to participants to coordinate meetings. Engagement-Focused Care Coordination will entail one to two visits, lasting 45-60 minutes each. PSE will involve six visits, each lasting 30-45 minutes. Meetings for either intervention can take place at home, during a work break, or at the clinic.

Follow-Up Procedures

Following randomization, follow-up assessments will occur every 2 months for 12 months. Follow-up assessors will be blinded to each subject's allocation. The study team will use the preferred methods of contact indicated by the subject upon enrollment (ie. phone calls, texts, email, etc). We will assess certain outcomes measures – depressive symptomatology, anxiety symptom relief, and engagement, retention, and satisfaction with mental health services – at 2 months, 4 months, 8 months, and 10 months by phone. We will assess all outcome measures at 6 months and 12 months in person. Assessment windows will be 6 weeks long: 2 weeks before the “expected date” and 4 weeks after the “expected date.” Due to the written consent form having been updated on 4/28/2018, follow-up will also include the reconsenting of participants that were enrolled and consented with the 8/10/2017 consent form.

Outcome Measure	Measured by:
Depressive symptomatology	QIDS
Symptom relief and behavioral activation	Beck Anxiety Index; Behavioral Activation for Depression Scale
Self-efficacy and coping skills	Brief COPE
Parenting Stress	Parenting Stress Index – Short Form; Perceived Stress Scale
Child behaviors	Child Behavior Checklist (CBCL-1.5/5)
Engagement, retention, and satisfaction with mental health services	Collaborative Psychiatric Epidemiology Survey; Client Satisfaction Questionnaire (CSQ-8)

10 Assessment of Safety and Data Safety Monitoring Plan (DSMP)

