Those opting to participate in the trial will meet with a study team member for written informed consent and for determination of final eligibility. Study participants must have no current source of mental health care and speak English or Spanish. Following confirmation of eligibility, the study staff member will administer a baseline survey that includes valid and reliable scales for depression and anxiety symptoms, trauma history and post-traumatic stress symptoms, history of receipt of mental health care, co-morbid substance use, and participant demographics. Mothers will then be randomized 1:1 to the two comparators, and followed for 12 calendar months.

Total Study Duration:	Three years
Subject Participation Duration:	One year

3 Background/Rationale & Purpose

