e. Child behaviors. Almost uniformly, our patient partners emphasize the impact of child behavior on their daily quality of life. For this, we will use the Child Behavior Checklist (CBCL-1.5/5) to assess a range of internalizing and externalizing child behaviors for children 1.5-5 years. We realize that not all participants will have children in this age range at all assessment time-points; thus, we have intentionally not powered the study with this measure.

An additional secondary outcome is engagement and retention with mental health services, as measured by NIMH's Collaborative Psychiatric Epidemiology Survey [18], which records all primary, specialty, and alternative sources of care. We categorize participants into those who engage with care; those retained in care; and those who receive evidence-based care. We use these definitions because of their association with a high likelihood of full symptom remission [5, 19, 20].

5 Study Design

We are conducting a randomized, parallel group comparative effectiveness trial of 230 pregnant and post-partum women with symptoms of depression. Women in one arm will receive Engagement-Focused Care Coordination, and women in the other will receive Problem Solving Education (PSE). Both intervention arms have been the subject of multiple BUMC IRB applications; all participant safety protocols have been tested over more than 10 years of related research.

In Engagement-Focused Care Coordination, the brief intervention is the Engagement Interview, which is designed to help engage participants in mental health care. The Engagement Interview is NOT a therapeutic or preventive intervention in and of itself. In delivering the Engagement Interview, Bachelor-level providers meet one to two times with women who screen positive for depression, and use techniques of shared decision-making to help mothers process the results of the screen; explore treatment options; and connect with formal mental health services. In PSE, problem solving sessions are one-on-one, workbook-based interactions that typically last 30 to 45 minutes. Sessions are delivered in the home, during lunch breaks from work, or in the clinic. A full course involves 6 sessions, delivered weekly or biweekly.

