We will employ stratified, blocked 1:1 randomization, the unit of which will be the mother. All investigators and data collectors will be blinded to study allocation. Randomization will occur independently at each clinic site (Prenatal Clinic, Pediatric Primary Care, Postpartum Unit). We will further stratify randomization by whether or not participants have previously received medication or therapy for depression, as this will likely impact treatment choices. Randomizing in blocks of randomly varying sizes of 2 and 4 within stratum will ensure balance between study arms.

Follow-up data collection will occur over the course of 12 month, with repeated collection of patient-centered outcomes by self-reported to research team members masked to intervention arm.

6 Potential Risks and Benefits

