12.3 Statistical Methods

Data Analysis Plan. We will report our results according to CONSORT guidelines. Because our aim is also for dissemination and implementation, we will analyze our data according to the RE-AIM (Reach, Effectiveness, Adoption, Implementation, Maintenance) framework, which addresses both internal and external validity.

- 1) **Reach.** We will record the number of mothers approached, screened, eligible, and refusing participation; compare demographics of those refusing to those participating; record subject attrition; and note all adverse events. We will compare baseline characteristics across comparators.
- 2) **Effectiveness.** We will conduct an intention-to-treat analysis to compare differences between comparators for all primary and secondary outcomes.

a) Main Effects. Our main effects analysis answers the question: **Which strategy is more effective at improving outcomes among a screened population of pregnant and postpartum women with depressive symptoms?**

- Patient Reported Outcomes: To assess depressive symptoms, we will employ Poisson or negative binomial regression techniques to compare incident rates of symptomatic episodes (QIDS ≥ 11) over 12 months of follow-up. We will use generalized estimating equations or mixed linear models to examine group-by-time effects on mean depressive symptom scores – as well as on mean scores of each of our other measures – as a function of intervention arm.

- Engagement and retention in care: Depending on the frequency of the observed outcomes, we will employ logistic or binomial regression techniques to compare the proportion of participants who meet the definition of engagement, retention, or receipt of evidence-based care. Among those engaging with care, we will employ Poisson or negative binomial regression techniques (depending on data dispersion) to compare number of mental health visits attended. We will compare treatment choices across groups. If data distribution assumptions are not met, we will consider nonparametric procedures or transformation of data. We will assess clustering by enrollment site and intervention practitioner, and if necessary use generalized mixed models to account for these effects. If randomization fails to produce balanced groups, we will add to our models potentially confounding variables, for which distributions are unequal across groups.

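### Section 7.1 admits a woman with one recent mental health appointment and further visits booked, which conflicts with the synopsis and could dilute the secondary engagement comparison

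*Combined protocol and SAP*

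**What the plan says.** Three places in the protocol bear on whether a woman already receiving mental health care can enroll.

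- The synopsis (Design/Methodology): "Study participants must have no current source of mental health care and speak English or Spanish".
- Section 7.1, inclusion criteria: "Woman had only one mental health care appointment in the last 3 months OR, if more than one appointment, woman has no upcoming appointments".
- Section 9, Screening Procedures. The outpatient record review collects, among other items, "mother's past and upcoming behavioral health appointments, and the visit type on the date of the EPDS screen". The verbal screen then asks "whether the mother is currently receiving behavioral health services, and her pregnancy status". A woman can be found ineligible on her answers, but the text does not say which answer about current services excludes her or how it relates to section 7.1.

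The outcome at stake is engagement and retention in mental health care, which is part of Objective 1 and a secondary outcome in section 4.2.2: "We categorize participants into those who engage with care; those retained in care; and those who receive evidence-based care". That section refers to definitions of these categories but does not set them out. Section 12.3 will "compare the proportion of participants who meet the definition of engagement, retention, or receipt of evidence-based care" and does not mention care already under way at baseline. Section 5 addresses treatment history through the randomization: "We will further stratify randomization by whether or not participants have previously received medication or therapy for depression". That factor is past treatment, not current care.

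**The concern.** The synopsis describes a population outside mental health care. The first limb of section 7.1 limits the number of recent appointments and says nothing about future ones. A woman seen once in the last 3 months with more visits arranged therefore meets section 7.1, yet plausibly has the current care that the synopsis rules out. The same limb, taken word for word, also fails to cover a woman with no appointments at all.

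This matters most for engagement. The Engagement Interview exists to connect women with services. A woman already connected at randomization would tend to be classed as engaged whichever arm she joins. Such women add to both proportions and reduce the difference between them.

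**Working it through.** **Eligibility, case by case.** The rule in section 7.1 is applied to past appointments in 3 months and to upcoming appointments, first literally and then with the first limb read as at most one.

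| Past | Upcoming | Literal | At most one | Against the synopsis |
|---|---|---|---|---|
| 0 | none | not admitted | admitted | belongs in the trial |
| 0 | booked | not admitted | admitted | not settled by the text |
| 1 | none | admitted | admitted | compatible |
| 1 | booked | admitted | admitted | conflicts |
| 2 or more | none | admitted | admitted | compatible |
| 2 or more | booked | not admitted | not admitted | compatible |

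The kinder reading repairs the zero-appointment rows. It does not change the row with one past visit and others booked, which is where the conflict lies.

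**The plan's own power figure.** Section 12.2 gives 100 analyzable women per arm, rates of 1.2 and 0.8 episodes, two-sided alpha 0.05 and 80% power. No power is stated for engagement. On the log rate ratio scale:

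- |ln(0.8/1.2)| = 0.405
- SE = √(1/(100 × 1.2) + 1/(100 × 0.8)) = √(1/120 + 1/80) = 0.144
- power = Φ(0.405/0.144 − 1.96) = 80.2%

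The stated figure reproduces. No input to it depends on care status at baseline.

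**Direction of the effect on engagement.** Let f be the share of each arm already in care, d the arm difference in engagement among women not in care, and d₀ the difference among women in care. The overall difference is (1 − f) × d + f × d₀. If women in care count as engaged in both arms, d₀ = 0 and the difference becomes (1 − f) × d. If the interventions still move engagement in the same direction among those women, the shrinkage is smaller.

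**Illustration only.** The documents give neither f nor engagement rates, so both are assumed here. With 40% and 60% engaged among women not in care and f = 10%:

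- one arm: 0.10 + 0.90 × 0.40 = 46%
- other arm: 0.10 + 0.90 × 0.60 = 64%
- difference: 18 points instead of 20

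Power is for a two-sided comparison of two proportions with 100 per arm:

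| f | Difference (points) | Power, 40% vs 60% |
|---|---|---|
| 0 | 20 | 81% |
| 5% | 19 | 77% |
| 10% | 18 | 73% |
| 20% | 16 | 64% |
| 30% | 14 | 55% |

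Over the same range of f, an assumed 30% vs 50% falls from 83% to 52%, and 50% vs 70% from 83% to 60%.

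**The case against.** The strongest reply is that section 7.1 is not the only gate. The verbal screen asks about current services, a woman can be excluded on her answers, and on the postpartum unit failing that screen makes her ineligible. The screening form is a listed study attachment (section 11.3) that is not reproduced, so it may contain a rule that turns these women away. This stands as a limit on how many are enrolled. It does not remove the conflict. If a yes excludes, the screen overrides section 7.1; if it does not, the synopsis is not met. The protocol text does not say which applies.

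A second reply is that the criterion is silent on upcoming visits for a woman with one appointment rather than openly permitting them, and that a single visit may not amount to being in care. That may be the intent. However, the condition on upcoming visits is written into the second limb alone, so a reader applying the text would admit her.

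Three stronger readings are tempting, and the documents do not support them.

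- A reader might infer that the trial shuts out its core group, women with no appointments. The synopsis names that group, randomization is stratified on whether women were previously treated, and section 12.2 expects 77% to meet full eligibility. All of this points to a drafting fault.
- A reader might infer that the second limb also admits women in care. Several past visits with none upcoming is compatible with having no current care.
- A reader might infer that sites apply different rules. The study team does the record review and verbal screening in both settings, and section 9 states that the postpartum population has the same criteria.

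Randomization also protects against bias between arms, and stratifying on previous treatment helps balance. Neither prevents dilution.

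**Conclusion.** The conflict between the synopsis and section 7.1 is real for a woman with one recent appointment and others booked. It survives the most favorable reading of the criterion, and section 9 does not settle it. The zero-appointment omission is a secondary wording matter.

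The consequence is established in direction only. To the extent that women already in care are enrolled and count as engaged regardless of arm, the engagement difference shrinks by the factor (1 − f). A reader might infer from the illustration that the engagement comparison loses a known amount of power. The documents do not support that: the share in care, the engagement rates and the operational definition of engagement are all missing, and a booked visit is not an attended one. The point concerns a secondary outcome and changes no sample-size or power figure stated in the plan.

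**What to change.** Reconcile the synopsis, section 7.1 and the screening text in section 9 into one rule. It should state what happens to a woman with no appointments and to a woman with one appointment and others upcoming, and how the verbal answer about current services is used. Which rule to adopt is for the sponsor.

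For women enrolled under the current wording:

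- derive care status at randomization from the chart review and from the care history in the baseline survey;
- adjust or stratify the engagement analysis by that status;
- add a sensitivity analysis limited to women not in care at baseline. Because the group is defined before randomization, the comparison stays randomized. The restriction is the step that removes the dilution from the difference in proportions.

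Counting only care first started after randomization would not serve instead. It would score women already in care as not engaged in both arms, so d₀ is again 0 and the same (1 − f) shrinkage remains.

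The cost is a short amendment, one derived variable and one extra analysis. On the postpartum unit, section 9 has appointment records reviewed only where available, so the baseline survey will have to supply care status for some of those women.
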